3.0 Intervention to be studied

General Methods for home-based delivery of taVNS +CIMT The goal of this discovery pilot project is to further develop the technical aspects of taVNS+CIMT delivery so that it is practical for delivery by a CIMT therapist in a home-based setting. This is essential to prepare for a treatment effectiveness study, which by necessity must be home-based because of the minimum 40-hour time commitment. First, we will use EMG sensors to automatically trigger the taVNS device, with the goal of decreasing the burden of treatment for the therapist. We will place the EMG sensors on major muscle groups on the shoulder and trunk and refine placement as needed to show that EMG-triggering can accurately and effectively trigger stimulation for 75% of total time spent in active movements. The therapist will still be able to manually trigger for other targeted behaviors (such as grasping). Once our placement of sensors has been tested and meets this designated threshold, the EMG-triggered system will be tested in home-based CIMT treatment.

The therapists providing the CIMT treatment are part of the study team. They have received specialized training in CIMT and the delivery of taVNS. These therapists were also a part of our original CIMT & taVNS study described above in section C1.2. They were part of the team who suggested the modifications of using EMG sensors to automate stimulation.

C2.1.1 Inclusion Criteria: Five 6–18 month-old infants, with hemiplegia/motor asymmetry qualifying for CIMT, Gross Motor Function Classification System (GMFCS) level I-IV, ability to maintain sitting position for 5 minutes with moderate assistance. **Exclusion Criteria:** Non-English literate parents, GMFCS level V, severe motor impairment/ quadriplegic involvement; uncorrected blindness or deafness, cardiomyopathy. Infants with cardiac issues will be cleared by cardiology before beginning treatment.

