C2.2.2 Targeted Muscle Groups We aim to automate 75% of stimulation time without significantly increasing the burden of system set-up/treatment delivery. We will use 2 sets of EMG sensors placed on the muscle groups activated in the vast majority of reaching and dynamic balance tasks.

- Reaching- Immature reaching in infants is initially driven by the biceps and triceps^{28,29}. As targeted reaching improves there is an increased use of the deltoids and upper trapezius as prime movers. Depending on the age/ability of the child we will target biceps brachii or anterior deltoid^{28,29}.
- Trunk control- EMG literature related to development of dynamic sitting balance indicates that thoracic level paraspinal muscles are most involved with emerging sitting balance and transitions to lumbar paraspinal activation as infants progress to more independent sitting balance²⁸⁻³⁰.

C2.2.3 Outcome measures for EMG automation taVNS stimulation is most effective when directly paired with active movements. Infant movement kinematics are characteristic of continuous movements rather than discrete movements. Since motions are not clearly discrete, we cannot count the number of stimulations and movements. Instead, a second therapist will record the time that the infant is actively engaged in movement tasks and compare that to the total time of taVNS stimulation, recorded by data acquisition modules in our taVNS set-up. One therapist will be delivering CIMT, a second therapist will be recording active movement time. For the first 2 participants, treatments will be completed in the research lab. This will allow the full team to be present, making sure that EMG triggered stimulation is occurring at the same time as active movement (the screen turns green when stimulation is on). If stimulation is not being delivered during active movement, modifications will be made to the system (e.g. changing amplification threshold for triggering, adjusting sensor location, etc). If total stimulation time is within 75% of total active movement time for therapy sessions in the first 2 infants, then we will transition CIMT delivery to the home-based setting for the final 3 infants.

C2.1.2 Treatment Delivery: CIMT-trained therapist with assistance from a research assistant will deliver CIMT for 40 hours (2 hours/day, 5 days/week for 4 weeks) +taVNS delivered via the BabyStrong (BS) system, (Soterix taVNS electric pulse generator unit & Neolead® electrodes).

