4.0 Study Endpoints

Primary Research Question: Can taVNS stimulation be automatically triggered during 75% of the total time for active infant arm and trunk movements during CIMT? **Primary Outcome measure:** Percentage of treatment sessions where total stimulation time was 75% of total active movement time.

Limitations and alternative approaches: *Trialing EMG system:* We will trial the EMG sensor system first with two healthy infants in the CHP laboratory setting to trouble shoot set-up and connection issues. The BSL and CIMT team will make any necessary modifications to the EMG-taVNS set-up. *Comparing total movement time to total stimulation time does not ensure stimulation is being provided at the appropriate time:* The stimulation device changes color when stimulation is being provided. Therefore, a second 'recording' therapist can monitor if the screen is green('on') when also recording active movement.

Aim 2: To generate proof of concept evidence demonstrating ability to provide high fidelity CIMT+taVNS treatment in a home-based setting in 3 infants. We will have a second therapist videotape CIMT therapy sessions while the CIMT therapist is delivering taVNS in the home with EMG triggered taVNS. We will randomly score 20% of sessions for CIMT treatment fidelity with published CIMT Fidelity tool. This aim will be completed with the final 3 participants after EMG set-up is finalized with first 2 participants.

Secondary CIMT+taVNS feasibility outcomes: Ability of therapist to operate taVNS easily and successfully by earning a "meet or exceed" score (3 or 4) on random therapy sessions by CIMT Fidelity Instrument. Ability of infant to tolerate wired ear electrode while remaining securely in place during sessions.

Secondary CIMT +taVNS efficacy outcomes: Change in the functional motor outcomes pre and post intervention on the *Quality of Upper Extremity Skills Test (QUEST)*

Title: Extending taVNS Paired with Infant CIMT into a Home-Based Setting: Technology Development Requisite for a Randomized Trial

PI: [name]

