8.0 Recruitment Methods

We have IRB approval for two pilot studies (#67997, #103800) in preterm and term stroke/HIE infants with taVNS paired with feeding using similar taVNS study procedures as proposed in this application. The taVNS system has a non-significant risk device designation from MUSC's IRB in these two pilot trials.

[name] will screen for infants in the nursery with known brain injury that will likely lead to hemiparesis or weakness, such as perinatal arterial stroke, HIE, severe IVH, PVL or cerebellar infarct, regardless of sex or race. The clinical team will inform the parents of the potential to

Title: Extending taVNS Paired with Infant CIMT into a Home-Based Setting: Technology

Development Requisite for a Randomized Trial

PI: [name]

participate in the study. [name] will then explain the study to the parents and give them contact information if they are interested, to initiate screening and consent procedures when their infant reaches 6-8months of age. Infants are also referred directly to [name] and [name] specifically for CIMT from a wide region of the southeast. Because some parents travel great distances to get these services, we may obtain referrals from other care providers out of our region. We will perform phone screening and obtain Econsent prior to patient arrival for patients whose parents cannot meet in person prior to the first treatment session, to be able to get services fully prepared for the visit. We will use the approved REDcap system to obtain consent. [name] or other approved study personnel will go over the entire consent document on the phone with the parent to ensure comprehension and to confirm identity. Parent will be given a copy of the completed, signed consent form in person or by email or fax.

Volunteers of all ethnicities and racial categories will be accepted into this study protocol. No preference will be given based on race, gender or ethnicity. Young infants who had perinatal complications leading to perinatally acquired brain injury may be considered vulnerable populations and are the target of this proposal.

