10.0 Study Design / Methods

Title: Extending taVNS Paired with Infant CIMT into a Home-Based Setting: Technology

Development Requisite for a Randomized Trial

PI: [name]

Overall Study Design: The goal of this discovery pilot project is to further develop the technical aspects of taVNS+CIMT delivery so that it is practical for delivery by a CIMT therapist in a home-based setting. This is essential to prepare for a treatment effectiveness study, which by necessity must be home-based because of the minimum 40-hour time commitment. First, we will use EMG sensors to automatically trigger the taVNS device, with the goal of decreasing the burden of treatment for the therapist. We will place the EMG sensors on major muscle groups on the shoulder and trunk and refine placement as needed to show that EMG-triggering can accurately and effectively trigger stimulation for 75% of total time spent in active movements. The therapist will still be able to manually trigger for other targeted behaviors (such as grasping). Once our placement of sensors has been tested and meets this designated threshold, the EMG-triggered system will be tested in home-based CIMT treatment.

This study will determine the feasibility of using EMG sensors to trigger taVNS stimulation paired with CIMT therapy in n=5, 6-18month old infants with hemiplegia after perinatally acquired brain injury. We will measure the effect of active taVNS paired with 40 hours of CIMT on infant motor skills before and after treatment over a month, and follow up the motor skills over 3 months. All infants will receive active taVNS treatment. CIMT treatment is a non-research procedure, and motor and developmental testing are non-research procedures. taVNS is a research procedure. CIMT sessions will be videotaped, to measure the fidelity of CIMT delivery while the therapist is delivering taVNS to determine feasibility.

The alternative treatment is the usual and customary occupational therapy services. If parents wish, they may pursue CIMT therapy with local therapists, but there are very few qualified therapists in the area. Also, although CIMT is considered a gold standard intervention, it is often not covered by insurance due to the time intensity required.

We will monitor for and mitigate following risks are present with this study: Risk of skin irritation, risk of discomfort, risk of slightly decreased heart rate, and risk of loss of confidentiality.

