15.0 Risks to Subjects

Risks of taVNS

taVNS is transcutaneous electrical stimulation of the auricular branch of the vagus nerve that innervates the ear. Although this novel therapeutic modality is still in the development and optimization process, few risks are expected by the peripheral taVNS in adults and infants. TENS devices are FDA approved for pain relief and are available over the counter. The main risks associated with TENS are electrical hazards that may result in user discomfort or injury. The unit used in these studies (Soterix) is a custom modified, FDA-cleared electrical stimulator that meets the standards of the FDA for investigational use. Skin irritation, redness, or inflammation may occur under the stimulating electrodes, but these have not been observed with short term use.

Two studies have used TENS on neonates to try to prevent or mitigate painful procedures (39-40). The TENS was administered at acupuncture sites with increasing current from 1-3.5 mA, and Hz from 2-10 in 30 healthy infants <3 days old. (39) In a subsequent study, this investigative team randomized 162 term neonates to TENS (3.5mA, 10Hz) or usual care to prevent pain from lancet heelsticks for blood sampling (40). These TENS parameters were safe and did not cause discomfort in the neonates. TENS has also been used with passive stretching in neonatal torticollis at 8Hz, 0.2mA for 30 minutes continuously (41) and in brachial plexus nerve injuries starting at 6 weeks of age to improve motor function of the hand, in conjunction with constraint induced movement therapy (42). Neither study reported adverse effects of electrical stimulation. TENS has also been used in peroneal and sacral nerve stimulation for dysfunctional voiding and stooling (44- 45). Finally, the routine sweat test employed in newborns and infants to confirm the diagnosis of cystic fibrosis uses transcutaneous electrical stimulation to deliver pilocarpine via iontophoresis (43). From the product brochure of the Nanoduct™ Neonatal Sweat Analysis System (Discovery Diagnostics, Canada), the nominal current is 0.5 (\pm 0.02) mA to 5 mA for 2.5 minutes (\pm 0.2 sec).

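### Do the inclusion lists in 3.0 and 5.0 admit infants outside the brain-injury population described in 10.0?

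*Combined protocol and SAP*

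**What the plan says.** Sections 3.0 (C2.1.1) and 5.0 share the same inclusion wording: infants aged 6–18 months "with hemiplegia/motor asymmetry qualifying for CIMT", GMFCS level I–IV, able to sit for 5 minutes with moderate help. Both exclude GMFCS level V and quadriplegic involvement. Neither gives a cause for the asymmetry.

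Section 10.0 describes the sample as "infants with hemiplegia after perinatally acquired brain injury". Section 8.0 says that infants with "perinatal complications leading to perinatally acquired brain injury may be considered vulnerable populations and are the target of this proposal". It gives two recruitment routes: nursery screening for known brain injury, and infants referred "specifically for CIMT from a wide region of the southeast". The second route carries no stated condition on cause.

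Section 4.0 defines the primary outcome as "Percentage of treatment sessions where total stimulation time was 75% of total active movement time". Treatment in 3.0 (C2.1.2) runs "2 hours/day, 5 days/week for 4 weeks".

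The exclusion text also differs. Section 3.0 lists parents who are not literate in English and calls for cardiology clearance where there are cardiac issues; 5.0 mentions neither.

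**The concern.** A statistician wants one definition of the population, because it settles to whom the result applies. Here the criteria that decide enrolment are wider, as to cause, than the sentence that describes the study. The direct-referral route does not close the gap.

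The protocol also shows that weakness without brain injury can be treated with CIMT: section 15.0 notes that TENS has been used "in brachial plexus nerve injuries starting at 6 weeks of age to improve motor function of the hand" alongside such therapy. An infant of that kind, within the age, GMFCS and sitting limits, would meet 3.0 and 5.0 but not fit 10.0.

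Three things would seem to be at stake:

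- **The trigger.** For reaching, section 3.0 (C2.2.2) states that "we will target biceps brachii or anterior deltoid", and the muscle signal after a nerve injury might differ from that after a brain injury.
- **The motor scale.** Section 2.0 (C1.2) describes QUEST as a test for children with cerebral palsy.
- **The weight of one infant.** With five infants, each counts heavily, most of all in the two-infant laboratory phase that decides the move to the home.

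**Working it through.** **1. The texts side by side**

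| Section | Function | Condition | Cause stated? |
|---|---|---|---|
| 3.0 C2.1.1 | Eligibility list | Hemiplegia or motor asymmetry suited to CIMT | No |
| 5.0 | Eligibility list | Same wording as 3.0 | No |
| 2.0 B | Background | Unilateral weakness | Not in that phrase |
| 8.0 | Recruitment | Names the target group | Yes, perinatal brain injury |
| 10.0 | Design summary | Hemiplegia only | Yes, perinatal brain injury |
| 15.0, 16.0 | Risks and benefits | Describes the subjects | Yes, perinatal brain injury |

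The two lists do not conflict on inclusion. They leave out a cause that four other sections supply. Section 10.0 is narrower in a second respect: it drops motor asymmetry and names hemiplegia alone.

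**2. The weight of one infant**

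Inputs: 5 days a week for 4 weeks at 2 hours a day (3.0, C2.1.2); two infants in the laboratory and three at home (6.0 and 7.0).

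- Sessions per infant: 5 × 4 = 20, which is 20 × 2 = 40 hours and agrees with the 40 hours stated.
- Full sample: 5 × 20 = 100 sessions. Laboratory: 2 × 20 = 40. Home: 3 × 20 = 60.
- One infant's share: 20/100 = 20% overall; 20/40 = 50% of the laboratory phase; 20/60 = 33% of the home phase.

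These are ceilings on the session counts, since enrolment is up to 5. They assume that every session is completed and that sessions are pooled across infants.

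If four infants meet the 75% ratio in X% of their sessions and the fifth meets it in none or all, the pooled figure lies between 0.8X and 0.8X + 20. With X = 80 (assumed), that is 64% to 84%. This range holds for any fifth infant, whatever the cause of the weakness. It shows how small the study is and says nothing about the missing cause.

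**3. How far the trigger depends on the arm muscle**

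- C2.2.2 specifies two sensor sets; the second is on the paraspinal muscles.
- The movement to be covered includes the trunk as well as the arm (4.0).
- The therapist can also trigger by hand, and the recorder logs stimulation from both sources (3.0, C2.1.2, item 4).
- C2.2.3 allows the triggering threshold and the sensor location to be adjusted when stimulation misses movement.

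A different signal in one arm muscle therefore need not carry through to the outcome. The documents give no figure for such an effect.

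**4. The exclusion text**

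Section 5.0 is silent on the two provisions in 3.0 and does not contradict them. A team that observes everything in 3.0 breaks nothing in 5.0. On language, 9.0 states that there will be no Spanish consent form.

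**The case for a change.** The strongest argument for acting is that enrolment is decided by the lists, and the lists never state the intended cause. Nursery screening requires a known brain injury; direct referral does not. Aligning the text would take one phrase in two places, and 10.0 already plans to collect head ultrasound and MRI results. With five infants, one misfit is a fifth of the data, and the pilot is meant to support a randomized trial in infant hemiplegia.

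The omission stands as a matter of wording, and so does the open second route. The rest carries less weight.

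- The brachial plexus reference in 15.0 is safety literature on electrical stimulation in other patients. It shows that the two wordings could in principle select different infants. It does not show that such infants will be referred here, and the documents give no number.
- QUEST is a secondary outcome in 4.0, and 12.0 declines a power analysis on the primary outcome with 5 participants.
- The obvious edit would not fully align the text. Adding the cause to 3.0 and 5.0 while keeping motor asymmetry would still differ from 10.0, which names hemiplegia only. The sponsor could equally widen 10.0.
- The collection of imaging results appears in 10.0 under confidentiality, not screening. The documents do not show that these results would be at hand when an infant from outside the region is screened, so a documentary requirement might cost places in a very small sample.

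**Conclusion.** The concern does not call for a change. The inclusion lists omit a cause that 8.0, 10.0, 15.0 and 16.0 state, and the investigators who screen infants for this specialist therapy can read the lists in that light. Nothing in the plan seeks infants with other causes.

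No statistical gain from an edit has been shown. The number of sessions, the definition of the primary outcome and the rule for moving to the home stay the same whichever wording prevails. One infant's 20% of all sessions, or 50% of the laboratory sessions, follows from enrolling five and would remain after any rewording. If an infant with another cause were enrolled, the record review listed in 10.0 should let the analysts say how many infants had a documented brain injury.

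The exclusion items missing from 5.0 are a clerical omission, and both lists can be observed together. They can be reconciled when the text is next edited.

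This conclusion assumes that the team screens for the stated target on both recruitment routes, and that the primary result is read as a description of triggering in a handful of infants, which is all that the plan's size supports.

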to trigger stimulation. Placing EMG sensors over key muscles in the shoulders and trunk we allow us to automatically detect when an infant is reaching or using their trunk to work on activities like sitting or rolling. By using EMG sensors we should be able to pair stimulation with movements reducing the burden on the therapist and allowing them to focus on facilitating a high quality treatment session. Automating the stimulation would make taVNS-paired CIMT more achievable in the home-based CIMT programs. Home-based delivery of CIMT is considered best practice for pediatric clients so families can be fully engaged, burden for families is reduced, and new skills can easily transfer to the natural environment for better carry over of treatment.

Qualifications

We have a unique collaboration of experts in brain stimulation, pediatric brain injury, translational clinical science and pediatric occupational therapy in this pilot project, and we are one of the few groups able to rapidly translate this neuromodulatory modality into home-based CIMT services. Refining the treatment protocol for home-based taVNS+CIMT and trialing incorporation of reliable taVNS triggering by this device we will provide us strong data to submit a grant for a randomized trial of home delivered taVNS+ CIMT in infant hemiplegia.

Study Aims

Aim 1: Investigate the feasibility of incorporating automatic triggering of the taVNS device using EMG sensors. *Rationale:* Manual taVNS triggering is mentally taxing for a therapist providing intensive, CIMT intervention. Movement based triggering would decrease the mental effort for using taVNS allowing the therapist to focus more on the treatment session. *Aim specific methods:* We will systematically test key muscle groups to see if EMG can be used to trigger taVNS stimulation at least 75% of the total time for active infant arm and trunk movements during CIMT. The first 2 participants will be completed in clinic to allow for updates to EMG system real time. After the first 2 participants complete the study we will trial the EMG system in the home setting for Aim 2.

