- 1) Hydrogel electrodes are placed in front of tragus and inner tragus/cymba chonchae, securing the wires behind head with tape. taVNS unit is attached to the baby using Velcro cummerbund (Fig.1, 2).

Title: Extending taVNS Paired with Infant CIMT into a Home-Based Setting: Technology Development Requisite for a Randomized Trial

PI: [name]

- 2) EMG electrodes will be placed on the shoulder (biceps/deltoid m) and on the trunk (paraspinus m) and connected to the taVNS unit via a wired interface.
- 3) CIMT and BSL therapists establish perceptual threshold (PT) daily, increasing slowly, until infant shows signs of tingling sensation. TaVNS is delivered at $0.1\text{mA} < \text{PT}$, $500\mu\text{sec}$, 25Hz, during each CIMT session, timed with movements of the weaker arm /trunk.
- 4) A CIMT therapist will deliver CIMT and use the manual trigger if needed for hand movements, while a second 'recording' therapist will record the active movement time. The Data Acquisition (DAQ) interface will record the amount of stimulation time and intensity from both EMG and manual triggering.
- 5) Good, moderate or poor impedance is constantly displayed on the taVNS unit. With poor contact, a beep sounds, and the electrode is adjusted.
- 6) Parent and OT will answer weekly questionnaire to assess their perception of ease of use, infant tolerance, and any recommendations for improvement of taVNS system or delivery.

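### The 75% target is stated on three different quantities, and because the primary outcome counts manual stimulation, a session can succeed without showing that triggering was automated

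*Combined protocol and SAP*

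**What the plan says.** All references are to the combined protocol and SAP. The 75% figure appears in three forms.

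- **Automated share of stimulation time.** Section 3.0, C2.2.2, introducing the muscle groups: "We aim to automate 75% of stimulation time without significantly increasing the burden of system set-up/treatment delivery".
- **EMG-triggered (automatic) time over active movement time.** Section 1.0, Aim 1, tests whether "EMG can be used to trigger taVNS stimulation at least 75% of the total time for active infant arm and trunk movements during CIMT". The General Methods in section 3.0 plan to "refine placement as needed to show that EMG-triggering can accurately and effectively trigger stimulation for 75% of total time spent in active movements", and section 10.0 repeats this. The research question in section 4.0 asks: "Can taVNS stimulation be automatically triggered during 75% of the total time for active infant arm and trunk movements during CIMT".
- **Total stimulation time over active movement time.** The rule in C2.2.3 for moving to the home begins "If total stimulation time is within 75% of total active movement time for therapy sessions in the first 2 infants". The primary outcome measure in section 4.0 is "Percentage of treatment sessions where total stimulation time was 75% of total active movement time".

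Manual triggering stays available throughout, for example for grasping (General Methods). Step 4 of C2.1.2 states: "The Data Acquisition (DAQ) interface will record the amount of stimulation time and intensity from both EMG and manual triggering". Read as written, total stimulation time therefore includes manual stimulation. No outcome in section 4.0 is split by trigger source.

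**The concern.** The three ratios answer different questions. The automated share says how much of the triggering the sensors took over. EMG coverage says how much of the infant's movement the sensors paired with stimulation. Total coverage says how much movement was paired by either route.

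Aim 1 and the research question are about automatic triggering. The outcome measure and the home-transition rule can be met partly, or even wholly, by the therapist pressing the trigger. Section 2.0 says that the therapist-triggered arrangement is not workable in the home, and removing it is the reason for the project. If manual use is substantial, the trial could report a high success percentage, and move to the home, without having shown what Aim 1 asks. A reader of the results could not tell, because nothing in section 4.0 separates the two sources.

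**Working it through.** The plan gives no figure to reproduce here: there is no expected value for any of the ratios, and section 12.0 says a power analysis is not valid with five participants. The check is on the definitions.

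**Notation.** E = EMG-triggered stimulation time, H = manually triggered time, S = E + H, M = active movement time. Each minute of stimulation is assigned to one source. The 75% is read as a minimum, as in Aim 1. The minutes below are assumptions for illustration; the documents give none.

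**Definitions.**
- C2.2.2: E/S ≥ 0.75
- Aim 1, General Methods, section 10.0, research question: E/M ≥ 0.75
- C2.2.3 rule, primary outcome measure: S/M ≥ 0.75

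**Illustrative sessions with M = 60 min.**

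| Session | E | H | S | E/S | E/M | S/M |
|---|---|---|---|---|---|---|
| 1 | 30 | 20 | 50 | 30/50 = 60.0% | 30/60 = 50.0% | 50/60 = 83.3% |
| 2 | 24 | 6 | 30 | 24/30 = 80.0% | 24/60 = 40.0% | 30/60 = 50.0% |
| 3 | 36 | 12 | 48 | 36/48 = 75.0% | 36/60 = 60.0% | 48/60 = 80.0% |
| 4 | 40 | 5 | 45 | 40/45 = 88.9% | 40/60 = 66.7% | 45/60 = 75.0% |

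All four keep stimulation within movement time (S ≤ M).

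- Session 1 succeeds on the primary outcome measure and fails both other targets; 20/50 = 40% of its stimulation is by hand.
- Session 2 meets the C2.2.2 target and fails both movement-time targets.
- Sessions 3 and 4 meet C2.2.2 and the outcome measure, but fail the research question. In session 4, five minutes of manual triggering turn a failure on EMG coverage into a success on the outcome measure.

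**General relations.**
1. Since S ≥ E, S/M ≥ E/M. Every session that meets the EMG-coverage target meets the total target, but not the reverse. The two disagree when E < 0.75M ≤ E + H, that is, when manual time covers at least the shortfall 0.75M − E.
2. If H = 0, E/S = 100% however little movement is covered, so the automated share alone does not establish coverage.
3. If S ≤ M, then E/S ≥ E/M. EMG coverage of at least 75% therefore forces an automated share of at least 75%. Within that condition these two ratios can disagree in one direction only: the share target met and the coverage target missed.

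**The case against.** The strongest reply is that no decision rests on C2.2.2. It is a one-line aim introducing the muscle groups. Sensor placement, the move to the home and the primary outcome are all judged against active movement time. This stands. A reader might infer from C2.2.2 that the sensor set could be accepted on the automated share while covering little movement. The documents give no such route, because the General Methods tie placement and the home step to movement time.

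A reader might also infer that a system with 75% EMG coverage could still fail the automated-share target because of heavy manual use. By relation 3 this requires more stimulation than recorded movement. For example, E = 48 and H = 20 give 68 min of stimulation in 60 min of movement. C2.1.2 intends stimulation to be timed with movement of the weaker arm and trunk. Whether hand movements such as grasping count as active movement time is not stated, so the case cannot be excluded, but the documents do not support asserting it.

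It can further be said that burden is addressed elsewhere: a weekly questionnaire to the parent and therapist covers ease of use, and a secondary feasibility outcome covers the therapist's operation of the device. That is fair, and the automated share reflects mental effort only indirectly. But neither measure records how much stimulation was manual, so neither answers the question about automatic triggering.

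Finally, this is a five-infant technology pilot with no powered test. That limits the weight of the point. It does not remove the mismatch between research question and outcome measure.

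**Conclusion.** The point holds as an inconsistency of definition with one practical consequence. The 75% target has three forms. The form used for the primary outcome and the home-transition rule includes manual stimulation, while the research question concerns automatic triggering. In the illustration, a session scores 83% on the outcome measure with 50% EMG coverage and a 60% automated share. How often this would happen cannot be said, because the documents give no expected amount of manual use. With none, the two movement-time ratios are identical.

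The conclusion rests on reading total stimulation time as including manual stimulation, which follows from C2.1.2 step 4 but is not spelled out in section 4.0. If the investigators meant EMG-triggered time only, the remedy is the same: say so. Rewording C2.2.2 alone would change no result and would leave the other two forms unreconciled. The comparator also varies (at least 75%, 75%, within 75%) and should be settled in the same edit.

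**What to change.** 1. State one target throughout: EMG-triggered stimulation time of at least 75% of active movement time. Use it in C2.2.2, in the C2.2.3 home-transition rule and in the section 4.0 primary outcome measure. Aim 1 already has this form; the General Methods, section 10.0 and the research question need only the words for a minimum.
2. In section 4.0, add as a separate secondary outcome the automated share, EMG/(EMG + manual), per session and per infant, and report total stimulation time over active movement time beside it.

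The cost is a few sentences and one extra summary by trigger source. Step 4 of C2.1.2 already provides for recording EMG and manual stimulation, so no new data collection is needed; the team should confirm that the log labels each source. The only downside is that fewer sessions may meet the target, since EMG coverage can never exceed total coverage.
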